## **12b. Power analysis**

Not applicable as this is an exploratory study we are not testing hypotheses because there are few data from which we can draw to estimate PrEP initiation among WWID (which highlights the gap in knowledge regarding this vulnerable population). However, we selected a target sample of 200 women based on the following data: estimating numbers from our pilot data collected from this population in which 86% of WWID expressed a willingness to use PrEP. We conservatively estimate that approximately 50% of those expressing willingness to initiate PrEP will do so. We also estimate 15% attrition at each study visit (based on previous experience with this population). Thus, we expect to have a final sample of approximately 122 WWID with 61 WWID in the PrEP initiation group and 61 in the declined group.

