**1. PROTOCOL TITLE:** Packaging PrEP to Prevent HIV Transmission among Women who Inject Drugs (WWID)

**2. IRB REVIEW HISTORY:** Approved 4/25/17; Modification 7 approved 07/06/2018

**3. OBJECTIVES/AIMS:** This study will address the following objectives or specific aims:

**Aim 1: To describe WWID's engagement in the PrEP care continuum.** Using data from baseline and exit (N=200), we will quantify participant engagement including: (1) attending initial clinical appointment; (2) enrolling in health insurance or medication assistance programs for uninsured participants; (3) accepting a PrEP prescription; (4) filling the PrEP prescription; (5) adhering to PrEP, and (6) returning for follow-up care. These activities represent critical moments when women could disengage or need additional support to remain in care.

**Aim 2: To assess the impact of predisposing, enabling, and need-related factors on WWID's engagement in the PrEP care continuum.** We will test for associations between Behavioral Model for Vulnerable Populations (BMVP) factors and stage of engagement.

**Aim 3: To explore how and why model factors are associated with WWID's decisions and ability to engage in PrEP care.** A subset of WWID representing those who never initiated PrEP (n=15), those who initiate but disengage (n=15), and those who adhere/return for 3 months (n=15) will complete an in-depth qualitative interview that explores individual and structural facilitators and barriers that support or hinder engagement. Interviews will draw on quantitative findings and provide contextual accounts of how factors operate, potential modification of service delivery and targets for behavioral interventions to support engagement.

**Aim 4. To describe sexual behavior and incident STI among WWID.** Using data from baseline, follow-up and exit (N=200), we will describe sexual risk behavior and acquisition of incident infections of syphilis, gonorrhea, chlamydia, and trichomoniasis among WWID. We will test for differences in risk/STI between those who initiated PrEP and those who did not.

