#### **10.e Retention**

To decrease attrition, we will develop a tracking protocol to ensure multiple points of contact with participants. Using their preferred mode of contact, we will remind participants of study visits and follow up with those who "no show." For each "no show," we will follow up twice weekly for 3 weeks. Any participant failing to contact staff within 3 weeks will be considered lost to follow up. However, they will not be withdrawn from the study. Using these procedures, we anticipate >85% retention.

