## 12. DATA MANAGEMENT

### 12a. Data analysis plan

**Aim 1. Describe WWID's engagement in the PrEP care continuum among WWID.** We will use summary statistics (frequency and percent with associated error terms) to describe participant engagement across key transition points in the care continuum including: (1) returning for STI results at T1; (2) enrolling in health insurance or medication assistance programs for uninsured participants between T0 and T2; (3) accepting a PrEP prescription; (4) filling the PrEP prescription or providing authorization for the PrEP prescription to be filled between T0 and T2; (5) adhering to PrEP between T1 and T3; (6) and returning for follow-up care at T2 and T3. Descriptive analyses will also be used to characterize adherence in terms of perfect defined as a dose of TFV within 48 hours (>1000 ng/mL), low adherence (>10 to >100 ng/mL), and non-adherence as defined by last dose more than one week prior (<10 ng/mL). We will also compare concordance of self-reported adherence to urinalysis.

**Aim 2. To assess the impact of predisposing, enabling, and need-related factors on WWID's engagement in the PrEP care continuum.** We will test the association between BMVP factors and WWID's engagement at each stage outlined above using procedures that have been used previously to describe gaps in the PrEP care continuum for MSM. Independent variables will represent each of the model's domains including: predisposing factors, enabling factors, and need (drawn from Table 1). In the case WWID do not populate each stage describe above we will collapse engagement into an ordered categorical variable similar to how we are approaching qualitative data. In this case, engagement would be treated as a 3-level variable: never initiated PrEP vs those who initiate but disengage vs those who remain engaged for 3 months. Inferential statistics will be used to identify associations between factors in the model and PrEP engagement. For

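### Outcomes measured only in women who attend are exposed to an expected loss of 28% by T2 and 39% by T3 that the planned percentages and error terms would not show

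*Combined protocol and SAP*

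**What the plan says.** Section 12b (Power analysis) states: "We also estimate 15% attrition at each study visit (based on previous experience with this population". From this it concludes that "we expect to have a final sample of approximately 122 WWID with 61 WWID in the PrEP initiation group and 61 in the declined group". The first 10.e section (Retention) gives another expectation, without naming a visit: "Using these procedures, we anticipate >85% retention". Of women lost to follow-up it says: "However, they will not be withdrawn from the study".

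In section 3, Aim 1 begins "Using data from baseline and exit (N=200", and Aim 4 attaches the same N to its baseline, follow-up and exit data.

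Section 12a analyses Aim 1 with "summary statistics (frequency and percent with associated error terms". Aim 2 compares women who do and do not engage at each stage, using t-tests, Mann-Whitney tests and chi-squared tests. Its fallback is a three-level outcome: never started PrEP, started then dropped out, or still engaged at three months. No denominator is given for any stage. There is no missing-data rule, no comparison of seen and lost women, and no sensitivity analysis. Section 12a contains no analysis for Aim 4.

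**The concern.** Loss to follow-up is closely tied to what is being measured. In the 12a list, stage 6 is attendance at T2 and T3. Self-reported adherence and urine drug levels are collected at T2, the latter only from women taking PrEP (10.b.vi). Acceptability, which section 9 names as an endpoint, is asked about only at T2 and T3. Follow-up behaviour and STI results likewise come only from women who attend.

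Followed as written, the plan yields either attenders-only figures or figures over 200 in which unseen women have no defined status. An error term for a percentage reflects sampling variation, not selection through loss. The results are meant to inform later study designs and sample sizes (12a) and a controlled trial (section 8), so an attenders-only adherence figure could be carried forward as if it described all women who started PrEP.

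**Working it through.** **Inputs.** 200 enrolled (section 6); 15% attrition per visit, 86% willing, 50% of the willing starting, and a final sample of about 122 (12b); more than 85% retention (10.e Retention).

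**Reproducing the plan's figure.** Compounding over T1, T2 and T3:
- T1: 200 × 0.85 = 170
- T2: 200 × 0.85² = 144.5, so 27.75% lost
- T3: 200 × 0.85³ = 122.8, so 38.6% lost (39% from the stated 122 of 200)

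The third line matches the plan's 122. This treats a woman who misses a visit as lost thereafter, as the plan's own figure does.

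**Bounds without assumptions about lost women.** If a share s of the cohort is seen and the percentage among them is p, the full-cohort value lies between s·p (no lost woman positive) and s·p + (1 − s) (every lost woman positive). The width is 1 − s whatever p is:
- T2: 0.72p to 0.72p + 0.28
- T3: 0.61p to 0.61p + 0.39
- 85% retained: 0.85p to 0.85p + 0.15

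**Comparison with the sampling error.** The documents give no exit rates, so the values of p below are assumptions. Half-width = 1.96 × √(p(1 − p)/n).

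| Setting | n seen | p (assumed) | 95% half-width | Full-cohort bounds |
|---|---|---|---|---|
| T2, 15% per visit | 145 | 25% | ±7.0 points | 18.1% to 45.8% |
| T2, 15% per visit | 145 | 50% | ±8.1 points | 36.1% to 63.9% |
| T3, 15% per visit | 122 | 25% | ±7.7 points | 15.3% to 54.3% |
| T3, 15% per visit | 122 | 50% | ±8.9 points | 30.5% to 69.5% |
| 85% retained | 170 | 25% | ±6.5 points | 21.3% to 36.3% |
| 85% retained | 170 | 50% | ±7.5 points | 42.5% to 57.5% |

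**Base for urine adherence.** The base is women who started PrEP, not 122 of 200. Section 12b assumes "86% of WWID expressed a willingness to use PrEP" and that "approximately 50% of those expressing willingness to initiate PrEP will do so", so 200 × 0.86 × 0.50 = 86 starters. At the same attrition, 86 × 0.85² = 62.1 are seen at T2 and about 24 are not. Fewer than 62 would be tested if some have stopped PrEP. If the 61 initiators in 12b's final sample are taken instead, 200 × 0.50 = 100 start (100 × 0.85³ = 61.4) and about 72 are seen at T2. The bounds are 28 points wide either way.

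**Aim 2's three-level outcome.** The roughly 24 unseen starters out of 86 have no assigned level: the plan does not say whether they are disengaged or missing.

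**Stages that do not need exit attendance.** For stages 1 and 6 in 12a, a woman who does not come is an observed non-returner. Acceptance is held in the study database (12b, data security). Insurance enrolment can be verified from case-management records (10.a, 10.b.ii). Fills are covered by the authorisation or pharmacy release in 10.b.iv. Section 10.b.viii also places the pharmacy release at T3, so fills are protected only if it is signed when the prescription is given.

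**The case against.** **Bias is not demonstrated.** This stands. A reader might infer that engagement is overstated by some 10 to 16 points and that the true value falls outside its own interval. That comes from assuming 50% engaged among 122 attenders and 10% to 25% among the 78 lost: (61 + 7.8)/200 = 34.4% and (61 + 19.5)/200 = 40.3%, against a lower limit of 50 − 8.9 = 41.1%. The documents give no rates for lost women. At an assumed 30%, the full-cohort value is (61 + 23.4)/200 = 42.2%, inside the interval. At T2 with 25% it is 0.7225 × 50 + 0.2775 × 25 = 43.1%, also inside 41.9% to 58.1%. A woman lost to visits may also still fill prescriptions at a pharmacy of her choice, so even the direction is not settled.

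**Most of the continuum is safe.** This also stands. A reader might infer that every engagement figure is compromised, but stages 1 to 4 and 6 can be determined for all eligible women from attendance and records.

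**The plan does foresee attrition.** In part this stands. Section 12b openly expects 122, and N=200 in section 3 can be read as the enrolled cohort, so the documents do not show that exit will be analysed as if 200 were seen. At 85% retention and p = 50%, the bounds equal the sampling interval. But the plan does not choose between its figures or carry either into 12a.

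**STI error terms.** A reader might infer that these are too narrow. Error terms appear only under Aim 1, and none is specified for STI results.

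**The study is exploratory.** This argues against elaborate modelling, but not against stating denominators. Section 3 plans a test of differences in Aim 4 and 12a plans tests in Aim 2.

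**Conclusion.** The point holds for outcomes that require attendance: stage 5 adherence, self-reported behaviour, acceptability, T2/T3 STI results, and the division between engaged and disengaged women in Aim 2's three-level outcome. On 12b's own attrition these rest on about 72% of women at T2 and 61% at T3. The uncertainty from loss is then 28 or 39 points wide, and the stated analysis would not display it. If 85% were retained it would be 15 points. The widths require no assumption about lost women; they assume only that the outcome is measured in every attender and that attrition compounds as 12b implies. For urine adherence the starter and attender counts also assume 12b's uptake rates and equal attrition in starters and decliners. The size and direction of any bias are unknown.

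**What to change.** 1. Reconcile N=200, more than 85% retention and 122: state 200 enrolled in Aims 1 and 4, and give one set of expected numbers seen at T2 and T3 (about 145 and 122 if 12b stands). Align the two lost-to-follow-up windows as well (three weeks under Retention, two weeks in section 14).
2. In 12a, report stages 1 to 4 and 6 over all women eligible for each, from study, pharmacy and PPP records. Count non-attenders as non-returners at stages 1 and 6.
3. For stage 5, take women who started PrEP as the base. Show three figures together: the attenders-only percentage, the percentage with unseen women counted as not adherent, and the upper bound.
4. For T2/T3 behaviour and STI results, and for Aim 2 outcomes needing T2/T3 data, compare T0 factors in seen and lost women. Add a sensitivity analysis weighting attenders by the inverse of their probability of attending, built from the T0 survey, T0 STI result and PrEP acceptance, and give the bounds beside it. State how unseen starters enter the three-level outcome.

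The cost is a few sentences in 12a and modest extra analysis, with no new visits or data. Reported ranges will be wider, and the adherence figure may look less favourable. Weighting corrects only for measured factors, which is why the bounds should accompany it.

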## **12b. Steps to be taken to secure data**

**Surveys** will be identified solely with a participant study ID number. Surveys will be completed in Qualtrics, an electronic survey platform available through Drexel One. In order to log into Qualtrics, users must provide a username and password. Further, the participants will complete surveys on a password protected laptop or tablet. Thus, these data are electronically secured. Access will be limited to only the study's PI and study staff. Client names linked to ID number will be in a separate locked file cabinet and only the PI and Research Coordinator will have access to this file.

**Qualitative interviews** will be identified using the same unique ID number that was assigned during the assessment. We will not collect participants' names or other identifying information. The unique ID that was assigned to the QBA survey we will link the qualitative interview information with the quantitative data for analyses.

The Qualitative Interviews will result in three pieces of information:

1. The digital audio recording file

2. A typed transcript of the digital recording
3. Hand- or computer-written notes from the interview

All of the information generated from the Qualitative Interview will be identified solely with the unique study ID number. Data generated from the Qualitative interviews will be maintained on password-protected Drexel University computer network server with access limited to only the study's PI and research staff using the same procedures for data security and backup outlined above.

**Risks to subjects** will be also minimized through staff ethics training, layered data security and by restricting access of sensitive information to staff members who have a specific need for the information.

- Training: All study staff are trained in the ethical treatment of study subjects and subject data with special emphasis on maintaining confidentiality.
- Data Security: All subjects will be assigned an identification number at the screening interview which will be used in place of names. All data files will be encrypted and password protected with passwords known only to the Principle Investigator and research staff.
- Restricted Access: Laptop computers will all be secured with password access and available only to study staff members. Laptops will be locked in cabinets in the secured study office when not in use.

Identifying information on participants will be on the consent forms and tracking forms. These forms will be kept in a locked filing cabinet in the PI or Research Coordinators office and will be separate from all other study-related data. Information from the tracking form and data relating to the management of participants will also be entered into and stored on the Drexel University College of Medicine secure, web-based solution designed to support data collection strategies for research studies — REDCap. The contact information will be stored in one study database separate from all other study-related data ((i.e., acceptance of a PrEP prescription, STI dx and related treatment, adherence call follow-up details) which will be identified with only the participant's unique study ID.

#### **12c. Procedures to control quality of collected data**

All staff will undergo extensive training on protocol. We will develop a checklist for each study visit to ensure consistency in data collection. The checklists (see Appendix 8) will detail the order of the appointment, forms to be completed, and specimen to be collected. Training will also included role-playing and mock interviewing. We will perform twice monthly review of subject files to ensure data completeness.

#### **12.d. How data and specimens will be handled study-wide**

- What information will be included in that data or associated with the specimens?
  - Urine specimens transported for Philadelphia FIGHT will be labeled only with participant unique study identifiers. Blood and swabs transported to the Philadelphia Health Department Laboratory will be labeled only with participant names per the requirements of health department and state law for reporting notifiable infections. On these specimens participant IDs will not be included; thus, linking between ID and name will be impossible.
- Where and how data or specimens will be stored?
  - Specimens will be stored in a locked case that only study personnel will have the keys to until they are transferred to an accredited laboratory for testing. Specimens going to FIGHT and to the Philadelphia public health lab will be transported in separate cases to ensure names and study ID numbers are separated.
- How long the data or specimens will be stored?
  - Specimens will be stored overnight in a lockable refrigerator and following testing the samples will be retained until the conclusion of the study. All data regarding subjects will be retained until the completion of the study and until manuscripts describing the data have been published.
- Who will have access to the data or specimens?

- Only members of the research team will have access to subject data. Philadelphia Department of Health will perform STI, Hepatitis B and creatinine testing. They are located at [name].
- Philadelphia FIGHT will perform drug-level monitoring. FIGHT is located at: located at [name]. Research team members will transport specimens to the lab for processing within 72 hours of their collection.
- Who is responsible for receipt or transmission of the data or specimens?
  - Principal Investigator ([name]) or co-Investigators ([name] and [name]) are responsible for receipt and transmission of the data/specimens.
- Will data be sent outside of the Drexel University system? **NO IF YES**
  - Where will the data be sent?
  - Why is it necessary to send the data outside of the Drexel University system?
  - How and in what format will the data be sent? (PHI must be encrypted).
  - How data and specimens will be transported?

### **13. Provisions to Monitor the Data to Ensure the Safety of Subjects**

This study is considered minimal risk as there is minimal risk associated with daily FTC/TDF as PrEP by HIV-uninfected individuals. Side effects during clinical trials included nausea, vomiting, abdominal pain, and diarrhea. These effects occurred in a minority of PWID (<20%) participating in the Bangkok Tenofovir Trial and most participants reported symptoms had resolved by the 2nd month. Of these side effects, only nausea and vomiting were statistically higher among PWID on Tenofovir than those taking the placebo. Tenofovir has been linked to renal impairment when used for HIV treatment, however, increased creatinine was observed in only 3% of patients in the Bangkok Tenofovir study.

Therefore a DSMB is not needed.

### **14. Withdrawal of Subjects**

During the consent processes, potential participants will be informed that the alternative to study participation is not to participate. They will be informed that their decision regarding participation will not affect their participation in PPP or Drexel University services. If a participant screens positive for HIV during the baseline appointment, the PI will remove the participant from the study. If participants choose to withdraw, all data collection will stop. Participants will receive relevant compensation for having attended the study visit if they choose to withdrawal.

As stated above, we will follow up with participants twice weekly for 2 weeks when they “no show” for an appointment. Any participant failing to contact staff within 2 weeks will be considered lost to follow up. However, they will not be withdrawn from the study.

### **15. Risks to Subjects**

Loss of Confidentiality: There is the possibility that participants' confidentiality could be compromised through the inadvertent loss of confidential information. Participants may experience loss of confidentiality if participant information is inadvertently shared with individuals not authorized to view it. To minimize this risk, all data collection will occur in a private space. A unique study identification number will be assigned to each participant and will be used to link participant quantitative surveys, audio-files, and transcription of the open-ended sections of semi-structured interviews with clinical records. On these data, the participant's identification number—not their name—will be used in the files to be analyzed.

Psychological Discomfort: There is the possibility that participants could experience psychological discomfort as a result of study questions during quantitative surveys or interviews relating to assessments of sexual behavior and drug use or if they were to receive a positive STI result during the study. We minimize the potential for psychological discomfort by informing participants that they are not required to participate in the study, that they should only share information they feel comfortable sharing, that they can refuse to answer any individual questions or withdraw from the study completely, and that there is no penalty for not participating.

We feel that these procedures will be effective in minimizing risks to the participants.

STI Testing: There is the minimal risk that participants could injure themselves through over-aggressive sample collection. We will minimize this risk by providing all participants instructions on how to collect their specimen. The literature shows that this procedure is acceptable to participants, is of minimal discomfort, has minimal safety risks (sample collection is considered non-invasive from a regulatory perspective), and provides reliable specimens.

Pregnancy: We will provide patients with contraceptive counseling and prescriptions as in the current standard of care for women per CDC PrEP clinical guidelines.

Toxicity: There is minimal risk associated with daily FTC/TDF as PrEP by HIV-uninfected individuals. Side effects during clinical trials included nausea, vomiting, abdominal pain, and diarrhea. These effects occurred in a minority of PWID (<20%) participating in the Bangkok Tenofovir Trial and most participants reported symptoms had resolved by the 2nd month. Of these side effects, only nausea and vomiting were statistically higher among PWID on Tenofovir than those taking the placebo. Tenofovir has been linked to renal impairment when used for HIV treatment, however, increased creatinine was observed in only 3% of patients in the Bangkok Tenofovir study. To monitor toxicity, we will measure creatinine levels at T1 and T2 (which will be scheduled over 3 months) as is recommended in the current CDC PrEP clinical guidelines and is considered standard of care.

